Appendix 3. Programming Specifications

1) Symptom alleviation and time to symptom alleviation

SIC questionnaire is shown in Appendix 2.

- 1. Targeted symptoms are those listed below. Only targeted symptoms will be evaluated in deriving of the secondary endpoint in time to COVID-19 symptom alleviation by Day 15.
 - Nasal congestion (stuffy nose)
 - Runny nose
 - Sore throat
 - Shortness of breath (difficulty breathing)
 - Cough
 - Feeling generally unwell (run down)
 - Fatigue (tiredness)
 - Physical weakness
 - Feeling faint
 - Muscle aches/pains
 - Joint aches/pains
 - Headache
 - Chills
 - Uncontrollable body shaking/shivering
 - Fever
- 2. Alleviation of all targeted symptoms:
 - Symptom with a rating of 0 at postbaseline
 - Symptom with a nonmissing rating at baseline has a decrease of at least 3 points in rating at postbaseline
 - Symptom with an answer "No" to the question at postbaseline

and

- for 48 consecutive hours (SAS datetime format dd:hh:mm:ss will be used for the duration)
 - A potential symptom alleviation is identified first without 48 consecutive hours confirmation. Participants with missing baseline symptoms data, all targeted symptoms need to have a rating of 0 or an answer "No" to the question for symptom alleviation.
 - Since the questionnaire recall time is over the last 24 hours, an additional consecutive 24 hours is needed to achieve consecutive 48 hours symptom alleviation, the reference start time of the second 24 hours is the assessment time of the first potential symptom alleviation.
 - No missing assessment is allowed between the first date and the last date of potential symptom alleviation included in the calculation.
 - The last day potentially able to meet the definition of alleviation is Day 14.

	Study Day									Day and			
Example		1	2	3	4	5	6	7	8	9		time of symptom alleviation	
1	Time		18:00	9:00	10:00								Day 3 9:00 to Day 4 10:00 ≥ 24 hrs
1	PSA		N	Y	Y	Y	Y	Y	Y	Y	Y	Day 3 9:00	
	Time			9:00	10:00								Day 3 9:00 to Day 4
2	PSA			Y	Y	Y	Y	Y	Y	Y	Y	Day 3 9:00	$10:00 \ge 24$ hrs, Missing symptoms on Day 2 has no impact.
3	Time		18:00	9:00	8:00	8:30							Day 3 9:00 to Day 4 8:00 <24 hrs, so check for next day Day 3 9:00 to Day 5 $8:30 \ge 24$ hrs
	PSA		N	Y	Y	Y	Y	Y	Y	Y	Y	Day 3 9:00	
4	Time		18:00	9:00	8:00	8:30	10:00	10:00					Day 3 9:00 to Day 4 8:00 <24 hrs, so check for next day Day 5 is not a PSA so need to check later date
	PSA		N	Y	Y	N	Y	Y	Y	Y	Y	Day 6 10:00	

Examples of counting additional 24 consecutive hours:

	Study Day										Day and		
Example		1	2	3	4	5	6	7	8	9		time of symptom alleviation	
	Time		18:00	9:00		9:00	10:00	10:00					no missing data is
5	PSA		N	Y		Y	Y	Y	Y	Y	Y	Day 5 9:00	allowed within consecutive 24 hrs, need to restart the clock; Day 5 9:00 – Day 6 10:00 ≥24 hrs
6	Time		18:00	8:00	8:00	8:30	10:00	10:00					Day 3 8:00 to Day 4 8:00 ≥ 24 hrs, symptom alleviation achieved even if symptoms reported on Day 5 Censored at Day 8 8:00 if prematurely discontinued from study after Day 8
	PSA		N	Y	Y	N	Y	Y	Y	Y	Y	Day 3 8:00	
7	Time		18:00	9:00	8:00	9:00	10:00	10:00	8:00				
	PSA		N	N	N	N	N	N	N				

PSA – potential symptom alleviation; Y – Yes; N – No; Yellow – symptom alleviation \ge 48 hours; Tan – symptom alleviation < 48 hours

Note: If a participant answered "No" to the question for all symptoms at baseline, alleviation status will not be derived, and the participant is excluded from the analysis.

If a participant had nonmissing results for symptoms at baseline and symptoms for Day 2 and later are all missing, the participant is considered as censored at 23:59 on Day 1.

If a participant has no SIC questionnaire data reported from Day 1 to Day 15, the participant is excluded from the analysis.

For all participants in ADEFF, the symptom alleviation status will be set to "Not Achieved Alleviation" with corresponding numeric value 0 at baseline, although symptom alleviation is not evaluated at baseline.

- 3. Time to alleviation of symptoms (unit = day, keep 8 decimals from date/time calculation in dataset, use 1 decimal place for TFLs)
 - For participants with symptom alleviation by Day 15, use the first event of participant level alleviation status equals Yes,

Date and Time of alleviation – Date and time of first dose.

• For participants who complete Day 15 of the study without symptom alleviation, time to symptom alleviation will be censored at Day 14,

Date and time of Day 14 SIC questionnaire assessment – Date and time of first dose.

Use Day 14 23:59 if no Day 14 SIC questionnaire assessment.

• For participants who have nonmissing results for symptoms for at least 1 day after Day 1 and discontinue from the study before Day 15 without symptom alleviation, time to symptom alleviation will be censored at the last SIC questionnaire assessment,

Date and time of last SIC questionnaire assessment – Date and time of first dose.

- For participants with missing time of first dose, missing time is imputed using the time of SIC questionnaire assessment on the first dose date or 12:00 whichever occurs first.
- 4. Additional censoring rules due to Intercurrent event:

Hospitalization for the treatment of COVID-19 or all-cause death or Use of rescue medication (see definition in #2)

Date and Time of Day 14 SIC questionnaire assessment – Date and time of first dose.

Use Day 14 23:59 if no Day 14 SIC questionnaire assessment.

2) COVID-19 Rescue Medications

Details of COVID-19 rescue medications are provided in the table below.

Drug Class	Dictionary Level	Prohibited PREF Codes	Prohibited Ingredient, PREF, and/or ATC Decodes	
Bamlanivimab and Etesevimab	PREF	15665101001	BAMLANIVIMAB;ETESEVIMAB	
Bamlanivimab	PREF	15343501001	BAMLANIVIMAB	
Bamlanivimab	PREF	15665101001	BAMLANIVIMAB;ETESEVIMAB	
Casirivimab and Imdevimab	PREF	15585401001	CASIRIVIMAB;IMDEVIMAB	
Cilgavimab and Tixagevimab	PREF	15616901001	CILGAVIMAB;TIXAGEVIMAB	
Molnupiravir	PREF	15326101001	MOLNUPIRAVIR	
Nirmatrelvir and Ritonavir	PREF	15892101001	NIRMATRELVIR;RITONAVIR	
Remdesivir	PREF	14269001001	REMDESIVIR	
Sotrovimab	PREF	15464401001	SOTROVIMAB	
Bebtelovimab	PREF	16033001001	BEBTELOVIMAB	
Ensitrelvir	PREF	16350701001	ENSITRELVIR	
Ensitrelvir	PREF	16350702001	ENSITRELVIR FUMARIC ACID	

ATC = anatomical therapeutic chemical; PREF = preferred

Additional medication may be included during final review of concomitant medications prior to data finalization.

3) Population, denominator, and numerator for efficacy endpoints summaries of proportion

Endpoint / Summary	Population / Denominator	Numerator
Proportion of COVID-19-related hospitalization or all cause death by Day 29 Proportion of participants with all-cause hospitalization by Day 29 Proportion of participants with COVID-19-related MAVs or all-cause death by Day 29 Proportion of participants with COVID-19-related MAVs by Day 29 Proportion of participants with all-cause death by Day 29	FAPS Based on KM estimate, no explicit denominator used	Total number of events by selected visits Note: Proportions from KM estimate differ from proportion calculated directly from number of event and participants at risk
Proportion of participants with negative SARS-CoV-2 nasal swab viral load at Days 3, 5, 10, and 15	Participants in the Virology analysis set who had SARS-CoV-2 nasal swab collected and nonmissing result of viral load reported at selected visits	Number of participants with negative SARS-CoV-2 nasal swab viral load
Proportion of participants with negative SARS-CoV-2 infectious viral titer at Days 3, 5, 10, and 15	Participants in the Virology analysis set who had SARS-CoV-2 nasal swab collected and nonmissing result of SARS-CoV-2 infectious viral titer reported at selected visits	Number of participants with negative SARS-CoV-2 infectious viral titer

4) Definition of Hospitalization

MAVs type of Emergency Room, non-ICU Hospitalization, ICU Hospitalization, and Hospitalization (unknown ward) could meet criteria for hospitalization if one of the following conditions is met:

- If the duration of the MAV is greater than 24 hours.
- If the duration is missing and end date of the MAV is 1 day after the start date.

Time to hospitalization is calculated as Start date of Hospitalization – First dose date + 1.

5) SARS-CoV-2 positive at baseline

SARS-CoV-2 positive at baseline is defined as test result from central lab.

- Cepheid's Xpert Xpress CoV-2/Flu/RSV plus (Multiplex) test result is positive for SARS-CoV-2 or
- SARS-CoV-2 RT-qPCR test result is numerical viral load result or "<2228cp/mL SARSCoV2 detected", regardless the sample was collected with less than specified volume of test solution.

GS-US-611-6273-Final Analysis-SAP-v1.0

ELECTRONIC SIGNATURES

Signed by	Meaning of Signature	Server Date (dd-MMM- yyyy hh:mm:ss)
PPD	Biostatistics eSigned	24-Jan-2024 01:01:34
PPD	Global Development Lead (GDL) eSigned	24-Jan-2024 17:55:34

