#### 4.2. Inclusion Criteria

Participants must meet all the following inclusion criteria to be eligible for participation in this study:

- 1) Aged  $\geq$  18 years at screening.
- 2) Willing and able to provide written informed consent, or with a legal representative who can provide informed consent (where locally and nationally approved).
- 3) SARS-CoV-2 infection confirmed by PCR or an approved alternative assay (eg, Rapid Antigen Test) ≤ 5 days before randomization. Serologic tests will not be accepted.
- 4) Initial onset of COVID-19 signs/symptoms  $\leq$  5 days before randomization with  $\geq$  1 of the following targeted signs/symptoms present at randomization.
  - a) Stuffy or runny nose.
  - b) Sore throat.
  - c) Shortness of breath (difficulty breathing).
  - d) Cough.
  - e) Low energy or tiredness.
  - f) Muscle or body aches.
  - g) Headache.
  - h) Chills or shivering.
  - i) Feeling hot or feverish.
  - j) Nausea.
  - k) Vomiting.
- CONFIDENTIAL

- l) Diarrhea.
- 5) Not currently hospitalized or requiring hospitalization.
- 6) Presence of  $\geq 1$  risk factor (if unvaccinated) or  $\geq 2$  risk factors (if vaccinated at any point) for progression to severe disease. Risk factors are the following:
  - a) Aged  $\geq$  50 years.
  - b) Current or recent ( $\leq 6$  months prior to randomization) cancer (other than localized skin cancer).
  - c) Have human immunodeficiency virus infection.
  - d) Prior splenectomy.
  - e) Prior solid organ, stem cell, or bone marrow transplant.
  - f) Have systemic rheumatologic or dermatologic disorders.
  - g) Use of systemic immunosuppressive agents, eg, high-dose corticosteroids (ie, ≥ 20 mg of prednisone or equivalent per day administered for ≥ 2 weeks), alkylating agents, antimetabolites, transplant-related immunosuppressive drugs, cancer chemotherapeutic agents classified as severely immunosuppressive, tumor necrosis factor blockers, other biologic agents that are immunosuppressive or immunomodulatory.
  - h) Have cerebrovascular disease.
  - i) Have cardiovascular disease, including heart failure, coronary artery disease, cardiomyopathies, and hypertension.
  - j) Have chronic kidney disease (provided participant does not meet exclusion criterion 7).
  - k) Have chronic lung disease (interstitial lung disease, pulmonary embolism, pulmonary hypertension, bronchiectasis, or chronic obstructive pulmonary disease)
  - 1) Have chronic liver disease.
  - m) Have cystic fibrosis.

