# 8. STATISTICAL CONSIDERATIONS

Details of the statistical methods will be provided in the statistical analysis plan, including any deviations from the original statistical analyses planned.

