# 8.5.2. Secondary Analyses

The secondary endpoints of COVID-19–related MAVs or all-cause death by Day 29 and all-cause death will be analyzed similarly as in the primary analysis. The secondary endpoints of all-cause hospitalization by Day 29 and COVID-19–related MAVs will be analyzed using a competing risk analysis approach, with death as the competing risk.

Medically attended visits are defined as any interactions with health care professionals other than study staff or designees including hospitalization; in-person emergency, urgent, or primary care visits; or any other in-person visit attended by the participant and a health care professional. The nature and cause of the visit should be identified.

All-cause hospitalization is defined as  $\geq 24$  hours of acute care, in a hospital or similar acute care facility, including emergency rooms or temporary facilities instituted to address medical needs of those with COVID-19. This includes specialized acute medical care units within an assisted living facility or nursing home. This does not include hospitalization for the purposes of public health and/or clinical study execution. The date and duration of hospital admission, and primary reason for hospitalization (including if the hospitalization is related to COVID-19) will be recorded.

A gatekeeping approach will be used for testing the key secondary endpoints. The endpoints will be tested in the following sequential order:

- Proportion of participants with all-cause hospitalization by Day 29.
- Proportion of participants with COVID-19-related MAVs or all-cause death by Day 29.
- Proportion of participants with COVID-19-related MAVs by Day 29.

Change from baseline in SARS-CoV-2 nasal swab viral load to Day 5 will be summarized by treatment groups and compared between treatment groups using a mixed-effects model repeated measures (MMRM) approach.

The Kaplan-Meier product limit method will be used to estimate, and log-rank test will be used to compare treatment groups for the time to symptom alleviation of targeted COVID-19 symptoms.

Handling of intercurrent events for key secondary efficacy endpoints is defined in Section 8.5.3.

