#### 11.5.1. Amendment 1 (29 March 2023)

Rationale for Key Changes Included in Amendment 1	Affected Sections	
Addition/modification of risk factors and targeted signs/symptoms of COVID-19 to inclusion criteria to align with Center for Disease Control and Prevention.	Synopsis and Section 4.2	
Overall clarifications and updates to inclusion/exclusion criteria resulting from queries received from sites and/or regulatory agencies.	Synopsis, Sections 4.2 and 4.3	
Additional relevant nonclinical toxicology, pharmacology, and PK language included based on Phase 1 drug-drug interactions and radiolabeled ADME. Consequently, restrictions on coadministration of acid-reducing agents were removed, hormonal contraceptive measures amended, and phototoxicity results demonstrating that GS-5245 is not considered a photosafety risk have been incorporated.	Sections 1.2.1.1.1, 1.2.1.1.1.1, 1.2.1.1.1.2, 1.2.1.1.2, 5.4.1, and Appendix 11.3	
Text updated regarding the clinical studies of GS-5245 to include latest available data including food effect data from Study GS-US-611-6248. Consequently, restrictions on administration of GS-5245 around food intake were removed.	Synopsis, Sections 1.2.1.1.3.1, 1.2.1.1.3.2, and 5.3	
Language updated regarding participants with compensated cirrhosis.	Sections 1.4.1 and 6.3.2.1	
Prior and concomitant medications that are prohibited was expanded to include ensitrelvir.	Section 5.4.1	
CCI	Sections 6.3.6, 6.3.6.1, 6.3.6.2, and 6.3.6.3	
Updates to secondary CCI objectives and endpoints to capture omissions (PK) and reflect additional analyses (PROs, viral titer, and coinfections).	Synopsis, Section 2	
Study drug discontinuation criteria clarifications and updated language (with corresponding inclusion criteria and toxicity management) for exclusion of participants with prior or current elevated bilirubin level.	Synopsis, Table 1, Sections 3.3.1.1, 4.3, 7.7.1.3, and 7.7.1.4	
Addition/clarification of efficacy analysis to include handling of intercurrent events.	Sections 8.5.1, 8.5.2, and 8.5.3	
Addition of definitions for medically attended visits and COVID-19–related hospitalization.	Section 8.5	
Minor changes to include clarifications or correct omissions/errors.	Throughout, as needed	

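### The SAP Appendix 3 Note that removes participants with no baseline symptoms does not say targeted symptoms, so read literally it keeps people with nothing to resolve, who can count as alleviated from Day 2

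*SAP*

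**What the plan says.** SAP 6.2 and SAP Appendix 3 give the same 15 targeted symptoms, all taken from the SIC questionnaire in SAP Appendix 2. Appendix 3 restricts the derivation to them: "Only targeted symptoms will be evaluated in deriving of the secondary endpoint in time to COVID-19 symptom alleviation by Day 15". A targeted symptom counts as alleviated after baseline if it is rated 0, has fallen at least 3 points from baseline, or is answered *No*. All 15 must meet this for 48 consecutive hours.

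Two rules in Appendix 3 deal with the baseline state. For missing baselines the text uses the qualifier: "Participants with missing baseline symptoms data, all targeted symptoms need to have a rating of 0" or a *No*. The Note, which concerns participants who report no symptoms at baseline, does not. It applies to a participant who answered *No* "to the question for all symptoms at baseline, alleviation status will not be derived", and that participant is left out of the analysis. Appendix 3 also sets everyone to not alleviated at baseline, "although symptom alleviation is not evaluated at baseline", so the earliest possible event is at the Day 2 diary.

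Protocol 4.2, inclusion criterion 4, requires at least one "of the following targeted signs/symptoms present at randomization" and then lists 12 items. Nausea, vomiting and diarrhea are among them, and any one is enough. Protocol 8.5.2 names the analysis as "time to symptom alleviation of targeted COVID-19 symptoms" and gives no list of its own.

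**The concern.** The Note exists to remove people for whom alleviation has no meaning because there is nothing to alleviate. That works only if the symptoms it checks are the symptoms the endpoint evaluates. As worded, it checks the whole questionnaire while the endpoint evaluates half of it.

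The gap matters because a participant can enter the trial with gastrointestinal symptoms alone. Such a participant answers *Yes* to a SIC item, so the literal Note does not exclude them. They also answer *No* to all 15 evaluated items, so they already satisfy every condition for alleviation. They would be counted as a very early event whether or not they recover.

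Two programmers working from this text could therefore analyse different participants. Under the literal reading, some events would reflect no recovery. The visible text of SAP 6.2 and 6.2.1 has no other rule that removes participants without baseline symptoms, so the Note carries this alone.

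**Working it through.** **Item count (SAP Appendix 2, legible text).** There are 25 items with a 0 to 10 rating, plus fever, shaking/shivering, smell, taste, and feet or toes: 25 + 5 = 30. Targeted items: 15. Non-targeted: 30 − 15 = 15, namely wheezing, sneezing, chest congestion, chest pain, brain fog, rash, eye irritation, diarrhea, vomiting, nausea, abdominal pain, loss of appetite, smell, taste, and feet or toes.

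**The SAP's own examples.** The Appendix 3 rule was coded as: take the first potential alleviation, require at least 24 further hours, allow no missing day. It returns the SAP's answers: Example 1, Day 3 9:00; Example 3, Day 3 9:00; Example 4, Day 6 10:00; Example 5, Day 5 9:00; Example 6, Day 3 8:00.

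**The same rule for a participant with vomiting only (constructed case).** Baseline: vomiting rated 7, *No* to all 15 targeted items. First dose: Day 1 12:00. Diaries: Day 2 09:00 and Day 3 10:00, with *No* to all 15 and vomiting still 7.

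- Literal Note: not excluded, because vomiting was answered *Yes*.
- Potential alleviation at Day 2 09:00. From there to Day 3 10:00 is 25 hours, which is at least 24, so it is confirmed.
- Time to alleviation = 21/24 = 0.875 day, with vomiting unchanged.
- Note read as targeted symptoms: the participant is excluded.
- List extended by nausea, vomiting and diarrhea (15 + 3 = 18 items): the participant is retained and not alleviated, since vomiting fell by 0 points.

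**How many people.** SAP 2.3 says that fewer than 50% of participants were randomized. Against the plan of 2300, that is fewer than 0.5 × 2300 = 1150. Each 1% is at most 0.01 × 1149 = 11.49, so 11 people. The documents give no count of gastrointestinal-only entrants.

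**Size of the effect, on assumed inputs.** None of these inputs is in the documents: exponential alleviation times seen at daily diaries, censoring at the Day 14 diary, placebo median 5, 7 or 9 days, alleviation hazard ratio near 1.2 or 1.5, 300,000 simulated participants per arm. The gastrointestinal-only share is equal in both arms, and each such person is an event at the Day 2 diary. Estimated hazard ratio by share:

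| Placebo median | 0% | 1% | 2% | 5% |
|---|---|---|---|---|
| 5 days | 1.199 | 1.196 | 1.194 | 1.187 |
| 5 days | 1.491 | 1.484 | 1.478 | 1.460 |
| 7 days | 1.197 | 1.194 | 1.192 | 1.184 |
| 7 days | 1.501 | 1.494 | 1.487 | 1.465 |
| 9 days | 1.196 | 1.193 | 1.190 | 1.181 |
| 9 days | 1.500 | 1.492 | 1.483 | 1.459 |

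The shift toward 1 is 0.003 to 0.008 at 1%, 0.005 to 0.017 at 2%, and 0.012 to 0.041 at 5%.

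**Against sampling error.** With 1:1 allocation, the standard error of the log hazard ratio is about 2/√(events). If all of 1149 participants had events, it would be 2/√1149 = 0.059; fewer events make it larger. The largest shift is ln(1.500/1.459) = 0.028, and 0.028/0.059 = 0.47, under half a standard error. For the 1% share in the same row, ln(1.500/1.492) = 0.0053, and 0.0053/0.059 = 0.09.

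**The case against.** The strongest reply is that the Note has a natural meaning. It follows an item titled for the alleviation of all targeted symptoms, which itself follows the sentence limiting the derivation to targeted symptoms. Elsewhere the block uses the bare word symptoms as shorthand, for example for missing baseline data and for missing diary days. The literal reading would also keep someone because of bruised-looking toes, which the derivation never evaluates. This stands as evidence of intent: targeted is the more likely meaning. It does not settle the text. The same block adds the qualifier in the missing-baseline rule, and a programming specification should not leave the analysed participants to inference. The intended reading also has a consequence that should be visible: a participant who met criterion 4 on gastrointestinal symptoms alone drops out of this endpoint.

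It is also fair to say that the effect is small and its size assumed. The simulation takes every gastrointestinal-only entrant as a Day 2 event, although some may develop a targeted symptom later, and nothing in the documents shows that such a participant exists. SAP 5.2 will tabulate the number of targeted symptoms at baseline, so a participant with none would show there, at least as a minimum of 0. All of this stands, and it is why the point is minor.

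A reader might go further and infer that leaving nausea, vomiting and diarrhea off the SAP list departs from the protocol and should be declared in SAP 6.5. The documents do not support that. Criterion 4 is an entry list, and the protocol never ties it to this endpoint. Protocol 8.5.2 lists no symptoms, and Protocol 8 hands over the detail: "Details of the statistical methods will be provided in the statistical analysis plan, including any deviations from the original statistical analyses planned". The SAP prints its 15 items openly, twice. The Amendment 1 log also records "Addition/modification of risk factors and targeted signs/symptoms of COVID-19 to inclusion criteria", and the earlier entry list is not in the documents, so a difference between the two lists says little about the endpoint.

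**Conclusion.** The wording of the Note needs correction. As written, it excludes on one set of symptoms and evaluates on another, and its literal reading admits events from Day 2 that involve no recovery. The likely intent is the targeted reading, but the text does not state it.

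The point is minor. The actual effect cannot be computed from the documents. On the assumed inputs above it is a shift toward 1 of at most 0.041 in the hazard ratio, at a 5% share. The direction toward 1 depends on the share being equal in the two arms. The endpoint is secondary and outside the alpha-controlled sequence in SAP 3.5; the primary endpoint and the four alpha-controlled secondary endpoints do not use this derivation.

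The 15-item list is a choice the SAP was free to make. Its one consequence worth keeping in mind is that ongoing nausea, vomiting or diarrhea cannot delay alleviation, so the result will not show whether those symptoms resolved.

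**What to change.** Reword the Appendix 3 Note so that it excludes participants who answered *No* to all targeted symptoms at baseline, where targeted means the list used in the analysis being run. This is in effect one added word and needs no new data. SAP Version 1.0 was signed in January 2024; if it is not to be revised, record the clarification in the clinical study report, as SAP 1 provides for changes after finalization.

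Optional: keep the 15-item analysis as specified and add one sensitivity analysis with the SIC nausea, vomiting and diarrhea items, 18 in all. These three are in the protocol's entry list and are already collected with 0 to 10 ratings. With the reworded Note applied to the 18 items, gastrointestinal-only entrants are retained and must improve to count. The cost is one extra derivation. For any participant analysed under both lists, the 18-item time can only be equal or longer, and the 18 items still match neither the 12-item entry list nor the 15-item list. No entry in SAP 6.5 is needed for the list.

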Table 3-2. Analysis Visit Windows for SARS-CoV-2 Mid-turbinate Nasal Swab

* If the nominal visit is a scheduled visit and the assessment is done on Day 4 (ie, Study Day = 4), assign to Day 3 or Day 5 analysis window based on the nominal visit label. If the nominal visit is an unscheduled visit or early discontinuation visit on Day 4, assign to Day 3 analysis window.

The analysis windows for hematology, chemistry, and coagulation laboratory tests are provided in Table 3-3.

Table 3-3.	Analysis Visit Windows for Hematology, Chemistry, and Coagulation
	Laboratory Tests

		Visit Window Study Day	
Analysis Visit	Nominal Study Day	Lower Limit	Upper Limit
Baseline	1	(none)	1
Day 3	3	2	4*
Day 5	5	4*	10
Day 15	15	11	22

* If the nominal visit is a scheduled visit and the assessment is done on Day 4 (ie, Study Day = 4), assign to Day 3 or Day 5 analysis window based on the nominal visit label. If the nominal visit is an unscheduled visit or early discontinuation visit on Day 4, assign to Day 3 analysis window.

The analysis windows for urine or serum pregnancy tests are provided in Table 3-4.

Table 3-4.	Analysis V	'isit Windows :	for Urine or S	Serum Pregnancy Tests
	v			0 1

		Visit Windo	w Study Day
Analysis Visit	Nominal Study Day	Lower Limit	Upper Limit
Baseline	1	(none)	1
Day 15	15	2	22

The Symptoms of Infection with Coronavirus-19 (SIC) questionnaire will be completed daily from predose at Day 1 to Day 15 visit, then at Day 29 visit. Windows are not assigned and results will be summarized for each applicable Study Day through Day 15. For the Day 29 nominal visit, the analysis window is provided in Table 3-5.

		Visit Windo	w Study Day
Analysis Visit	Nominal Study Day	Lower Limit	Upper Limit
Baseline	1	(none)	1
Day 29	29	24	34

Table 3-5. Analysis Visit Windows for the SIC Questionnaire

3.8.3. Selection of Data in the Event of Multiple Records in an Analysis Visit Window

Depending on the statistical analysis method, single values may be required for each analysis window. For example, change from baseline by visit usually requires a single value, whereas a time-to-event analysis would not require 1 value per analysis window.

If multiple valid, nonmissing measurements exist in an analysis window, records will be chosen based on the following rules if a single value is needed:

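### Participants who complete Day 15 but stop the symptom diary early are censored at Day 14, so unobserved days count as days without alleviation

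*SAP*

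**What the plan says.** Time to COVID-19 symptom alleviation by Day 15 is listed in SAP section 6.2 under other secondary efficacy endpoints. Section 6.2.1 analyses it by Kaplan-Meier and a stratified log-rank test, with a Cox hazard ratio. Alleviation is derived from the daily SIC questionnaire and needs confirmation over 48 hours. Appendix 3 adds: "No missing assessment is allowed between the first date and the last date of potential symptom alleviation included in the calculation".

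The censoring rules are in Appendix 3, item 1.

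- Completers: "For participants who complete Day 15 of the study without symptom alleviation, time to symptom alleviation will be censored at Day 14". The time is that of the Day 14 assessment, with the fallback "Use Day 14 23:59 if no Day 14 SIC questionnaire assessment".
- Participants with at least one diary day after Day 1 who "discontinue from the study before Day 15 without symptom alleviation, time to symptom alleviation will be censored at the last SIC questionnaire assessment".
- Participants with baseline data only: if "symptoms for Day 2 and later are all missing, the participant is considered as censored at 23:59 on Day 1".
- No diary at all: "If a participant has no SIC questionnaire data reported from Day 1 to Day 15, the participant is excluded from the analysis".

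Table 6-1 also assigns Day 14 to COVID-19 hospitalization, death and rescue medication, where it explicitly stands for never achieving alleviation. Stopping the diary is not in that table.

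**The concern.** Once the diary stops, no alleviation can be recorded or confirmed, so observation of this endpoint has ended. For completers the SAP ties censoring to study completion instead. The fallback to Day 14 23:59 shows that the rule is meant to cover people with no diary at the censoring time. The days between the last entry and Day 14 then enter the analysis as observed, event-free time. In effect, missing diaries are treated as persistent symptoms, without that assumption being stated.

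At stake are the Kaplan-Meier medians and the proportion alleviated in both arms and, if diary stopping differs between arms, the hazard ratio and log-rank comparison.

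**Working it through.** The documents give no median, hazard ratio, power or diary-missingness rate for this endpoint, so there is no planned figure to reproduce.

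**1. The same diary under the written rules** (no alleviation derived, no composite event)

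| Diary entries present | Leaves study before Day 15 | Completes Day 15 |
|---|---|---|
| Day 1 only | Day 1 23:59 | Day 1 23:59 |
| Days 1 and 2 | Day 2 entry | Day 14 23:59 |
| Days 1 to 8 | Day 8 entry | Day 14 23:59 |
| Days 1 to 14 | Day 14 entry | Day 14 entry |

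Example 7 in Appendix 3 confirms the Day 8 result for a discontinuer. Among completers, one extra entry on Day 2 moves censoring from Day 1 to Day 14. Completers with a full diary, and anyone whose alleviation was confirmed before the diary stopped, are unaffected.

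**2. Effect on the proportion and median, by formula**

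Assumed, not from the documents: exponential times with medians 10 days (placebo) and 8.5 days (active), and a fraction p of completers stopping the diary at a time S uniform on Days 2 to 10, unrelated to recovery.

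- λ = ln 2 / median: 0.06931 (placebo), 0.08155 (active). Hazard ratio for alleviation = 10/8.5 = 1.18.
- Full data: F(14) = 1 − exp(−14λ) = 62.1% and 68.1%.
- Chance that a stopper's alleviation precedes the stop: 1 − [exp(−2λ) − exp(−10λ)]/(8λ). Placebo: 1 − (0.8706 − 0.5000)/0.5545 = 0.332. Active: 1 − (0.8495 − 0.4424)/0.6524 = 0.376.
- Day 14 rule, p = 20%: placebo 0.8 × 0.621 + 0.2 × 0.332 = 56.3%; active 0.8 × 0.681 + 0.2 × 0.376 = 62.0%.
- Placebo median: solve 0.8 F(t) + 0.2 × 0.332 = 0.5. F(t) = 0.542, so t = −ln(0.458)/0.06931 ≈ 11.3 days. Simulation gave 11.2. The active median rises from 8.5 to about 9.3 days.

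**3. Hazard ratio, by simulation** (same assumptions, 200,000 per arm or more)

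| Stopping, placebo/active | Day 14 rule | Last-diary censoring |
|---|---|---|
| none | 1.17–1.18 | 1.17–1.18 |
| 20%/20% | 1.17 | 1.17–1.18 |
| 20%/10% | 1.24–1.25 | 1.17–1.18 |
| 10%/20% | 1.10 | 1.17–1.18 |
| 12%/8% | 1.20–1.21 | 1.18 |

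**4. Other inputs**

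With a placebo median of 8 days, random stopping over Days 1 to 13 and 20,000 per arm, the placebo median rises by about 0.3 day at 10% stopping, 0.55 day at 20% and 0.95 day at 30%. The placebo proportion alleviated falls by about 2.5, 5 and 8 points. With no true effect, unequal stopping (20%/10% or 10%/20%) moves the hazard ratio from 0.99 to 1.05 or from 1.02 to 0.96.

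**5. Stopping because of recovery, just before confirmation**

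- Placebo median 8 days, 20% stopping in both arms: full data 8.01 days, Day 14 rule 10.76, last-diary censoring 9.75.
- Medians 10 and 8.5 days: with 20%/10% stopping, the Day 14 rule gives 1.34–1.39 and last-diary censoring 1.30–1.34. With 10%/20% they give 0.97–1.01 and 1.04–1.06. The full-data value is 1.18. The ranges reflect runs that placed the stop and the horizon slightly differently.

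**The case against.** Day 14 is the last day on which the definition can be met, so it is the natural end of follow-up for a completer with a full diary. SAP section 3.6.1 allows specified missing-data methods, and Appendix 3 specifies one. If diary-stoppers really stayed symptomatic, the rule would be right. With balanced stopping the hazard ratio barely moves, and the larger shifts need a twofold difference in stopping between arms of a double-blind trial. All of this stands. It limits the size of the problem, but it does not explain why identical diaries are censored differently by study completion.

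Four stronger readings are tempting, and the documents do not support them.

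- A reader might infer that Table 6-1 reserves Day 14 censoring for composite events. It does not say so; it simply does not list diary stopping.
- A reader might infer that a Day 15 visit held on Day 13 ends the diary early, because SAP section 3.8.2 says the "questionnaire will be completed daily from predose at Day 1 to Day 15 visit". The schedules in both documents require daily entries through Day 15, so at most the wording is ambiguous.
- A reader might infer that this is the trial's only symptom analysis. It is the only symptom endpoint among the listed secondary endpoints, but exploratory objectives and part of SAP section 6 are redacted. For the same reason, the lack of a visible sensitivity analysis does not prove that none is planned.
- A reader might infer that last-diary censoring cures the bias. Step 5 of the working shows that it does not when people stop because they feel well.

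**Conclusion.** The concern holds. The Day 14 rule keeps completers with an abandoned diary at risk when no event can be recorded, and it conflicts with the handling of discontinuers and of those with no diary after Day 1. If any such participants recovered unobserved, the direction is certain within each arm: longer times and a lower proportion alleviated. Under random stopping of 20% in both arms, this is about 0.5 to 1.3 days on the placebo median across assumed medians of 8 to 10 days, with little change in the hazard ratio. The hazard ratio is materially affected only if stopping differs by arm, and it can then move either way.

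The size cannot be fixed from the documents, and every figure rests on the assumed times and stopping patterns. The endpoint is outside the alpha-controlled sequence, so no primary or key secondary test is touched. The change should be made, but the trial's main conclusions do not depend on it.

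**What to change.** In SAP Appendix 3, item 1, part 3:

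- Censor every participant who has at least one SIC assessment after Day 1, no alleviation and no composite intercurrent event at the last nonmissing SIC assessment on or before Day 14, whether or not Day 15 was completed.
- Keep Day 1 23:59 for those with no diary after Day 1. Without this exception, a predose Day 1 entry would give a negative time.
- Keep Day 14 censoring for hospitalization, death and rescue medication.
- Report diary missingness by arm and day.
- Keep the current Day 14 rule as a sensitivity analysis, labelled as assuming that stoppers remain symptomatic.

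The cost is a small wording and programming change, plus one extra analysis and one table. Somewhat less follow-up time is counted. The main downside is that last-diary censoring assumes stopping is unrelated to recovery, so it should be read alongside the missingness table. If the data are already finalized, run the last-diary version as an added sensitivity analysis and document it in the CSR, as SAP section 1 provides for later changes.
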